11.3 Statistical analysis of secondary end points

For the secondary outcomes, time-to-event analysis, such as survival analysis will be used to determine differences in time to first episode of delirium. Delirium precipitants, which occur at variable times and for different durations during the study period are time-dependent covariates and Cox proportional hazard modelling will be used.

The incidence rate of delirium will also be calculated and compared between the treatment and control groups. For possible toxicity of the medication, incidence of adverse event will be calculated and reported.

11.4 Health economic analyses

Limited evidence suggests that interventions to prevent delirium or reduce its duration in hospital are cost effective, ^{57,58} with the majority of cost offsets from longer term care savings. ⁵⁷ Estimating cost offsets over shorter time frames is crucial given advanced cancer has limited prognosis, and in prior cost-effectiveness studies, patients with terminal illness were excluded. ³⁴ The cost-effectiveness sub-study will evaluate the within-study incremental resource use, cost and consequences of melatonin relative to placebo for preventing delirium in advanced cancer patients from randomisation to study end or death (whichever is sooner). The analysis will include efficacy (delirium-free days), toxicity, survival and resource data (intervention costs, hospital length of stay, health professional time, medication use and investigations). Sampling and parameter uncertainty will be

estimated by bootstrapping on participants' costs and effect pairs to maintain covariance in re-sampling with replacement across 10,000 replicates. Cost-effectiveness acceptability curves, sensitivity and scenario analyses will be undertaken.

11.5 Power and sample size

Sample size was calculated based on the information obtained in the pilot study on the primary outcome, namely delirium-free days during a 3 week study period, and an analytical approach of comparing the mean delirium-free days between groups. It has been estimated that a sample size of 110 in each arm (n=220 in total) would provide 90% power to reject the null hypothesis with a 5% type I error rate to detect an increase of 2 delirium-free days allowing for 30% drop out or loss to follow-up and 5% for possible adjustments for covariates.

11.6 Interim analyses

Two planned interim analyses will be conducted independently and reviewed by the independent data and safety monitoring committee after about 33% and 66% of patients have been enrolled. The primary outcome and adverse events will be compared between groups with p<0.001 required as the threshold of stopping the trial for significant evidence of benefit or harm in either one of the treatment arms.

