9.7 Stopping rules

The study will be stopped if new literature indicates findings that can be applied to this question in terms of benefit or side effects, or if reporting of adverse events indicate that review of the study protocol is required, for either or both of the study drugs, or rescue medicine. Two planned interim analyses will be conducted independently and reviewed by the independent data and safety monitoring committee after about 33% and 66% of patients have been enrolled. The primary outcome and adverse events will be compared between groups with p<0.001 required as the threshold of stopping the trial for significant evidence of benefit or harm in either one of the treatment arms.

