10.2 Data Safety Monitoring Committee

This study will have a contracted independent Data Safety Monitoring Committee (DSMC). The primary role of the DSMC will be to monitor adverse and serious adverse events. All adverse and serious adverse event reports will be reviewed at 6 monthly intervals, as agreed by the DSMC. In addition, any emerging safety issues will be reviewed by the DSMC on an ad hoc basis if required.

The Data Safety Monitoring Committee (DSMC) will be established to:

- review data from an ethical standpoint, with patient rights, safety and wellbeing being paramount
- consider data from interim analysis where such an analysis is planned
- report on trial continuation

Reports will be provided to the PaCCSC Management Advisory Board and Scientific Committee.

The Data Safety Monitoring Committee (DSMC) will consist of:

- experts in field
- a clinical trials statistician
- a trial pharmacist
- an experienced palliative care physician.

Specifically, the DSMC will receive serious adverse events as part of the established reporting mechanism (email notification of the report from the coordinating site within 24 hours) if the event is unexpected and related to the study intervention. In addition, the DSMC will receive a summary report of all adverse events, these will be discussed as a standing agenda item, with the discussions, actions and outcomes recorded. The DSMC will also receive an updated literature summary at each meeting, which will address new published literature that may have an impact on the study.

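### The interim rule sets the same p<0.001 for harm as for benefit, which makes it insensitive to uncommon adverse events and leaves it unreconciled with the safety routes in 9.7 and 10.2

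*Protocol*

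**What the plan says.** Section 11.6 plans two looks, "after about 33% and 66% of patients have been enrolled". At each, "The primary outcome and adverse events will be compared between groups". The condition that the section then sets for ending the trial early reads "p<0.001 required as the threshold of stopping the trial for significant evidence of benefit or harm in either one of the treatment arms". Section 9.7 (Stopping rules) and the analysis paragraph of the trial summary carry the same rule. The threshold is therefore symmetric and covers adverse events as well as delirium-free days. No separate harm boundary and no expected adverse event rate are given, and the protocol does not say whether the p-value is one- or two-sided.

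Two other places bear on stopping for safety, and neither uses a p-value:

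- Section 9.7, just before the interim rule, says the study will be stopped if adverse event reporting shows that the protocol needs review.
- Section 10.2 gives the committee six-monthly review of all adverse event reports and ad hoc review of emerging safety issues. It puts patient safety first and asks the committee to "report on trial continuation".

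Section 11.5 sets the trial size: "a sample size of 110 in each arm (n=220 in total) would provide 90% power".

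**The concern.** A threshold as strict as p<0.001 at an interim look has one main job: to stop early looks from using up the type I error of the final efficacy test. A comparison that stops the trial for harm leads to no claim of benefit, so loosening it costs nothing on that account. Carrying the efficacy threshold over to adverse events makes the harm side strict without the usual reason, at looks where the arms are small.

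The wording adds to this. The threshold is *required* for stopping, while 9.7 and 10.2 describe safety routes with no such condition. A committee facing a marked imbalance that falls short of p<0.001 would find one sentence pointing to continuation and others pointing to its own judgement, with no statement of which takes precedence.

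**Working it through.** **Inputs from the protocol.** Total 220, 110 per arm (11.5); looks at about 33% and 66% enrolled (11.6); threshold p<0.001 (11.6, 9.7).

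- First look: 0.33 × 220 = 72.6, about 36 per arm.
- Second look: 0.66 × 220 = 145.2, about 73 per arm.

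The protocol states no operating characteristic for the interim rule, so there is no figure of its own to reproduce.

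**Assumptions.** The background event rate is not in the protocol, so a range is shown. The threshold is taken as two-sided and the test as Fisher's exact. Every enrolled patient is counted, which is generous.

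**Method.** With n per arm, background rate p and tripled rate 3p, the probability of triggering is the sum, over all pairs (a, b) with b > a and Fisher p below the threshold, of Bin(a; n, p) × Bin(b; n, 3p). This is exact enumeration, counting only the harm direction.

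**Probability that a true tripling reaches p<0.001**

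| Background → tripled | First look, 36 per arm | Second look, 73 per arm |
|---|---|---|
| 5% → 15% | 0.6% | 4.9% |
| 10% → 30% | 6.8% | 34% |
| 15% → 45% | 24% | 72% |
| 20% → 60% | 51% | 95% |
| 25% → 75% | 83% | >99% |

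If 30% are lost, the drop-out allowance in 11.5, about 25 per arm are evaluable at the first look (0.70 × 36 = 25.2). The 10% → 30% figure then falls to 2.4% and the 20% → 60% figure to 25%.

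**What the threshold means in counts.** With 36 per arm, the smallest splits reaching p<0.001 are 0 v 10, 4 v 18 and 7 v 22. A split of 4 v 17, or 11% v 47%, gives p = 0.0015 and does not meet it.

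**Effect of a looser threshold on the harm side**

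| Scenario | p<0.001 | p<0.01 | p<0.05 |
|---|---|---|---|
| 36 per arm, 5% → 15% | 0.6% | 3.8% | 14.6% |
| 36 per arm, 10% → 30% | 6.8% | 23.4% | 47.2% |
| 73 per arm, 10% → 30% | 34% | 63% | 82% |

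**Price of the looser threshold.** With no true difference and a background of 10% to 20% in both arms, the chance of a harm-direction p<0.05 is about 0.7% to 1.5% per event per look. Over both looks it is about 1.7% to 2.4% per event. Section 9.3.2 lists seven symptoms of interest. If all seven were tested and behaved independently, the chance of at least one false prompt would be 1 − (1 − 0.017)^7 = 11% to 1 − (1 − 0.024)^7 = 16%.

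**The case against.** **Safety does not rest on this p-value.** Section 9.7 provides for stopping when adverse event reports show that protocol review is needed. Section 10.2 gives the committee regular and ad hoc safety review and does not make its advice depend on p<0.001. A reader might infer from the interim rule that the trial cannot be stopped for harm short of p<0.001, or that safety stopping is in effect missing. The documents do not support that. What remains is narrower: nothing says how the required threshold relates to these other routes.

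**The event rate is assumed.** A reader might also infer that even a tripling of an adverse event would almost never trigger the rule. That is fair at a 5% background at the first look, and at 10% the chance is low. It is wrong for common events, where the first-look chance is 51% from 20% and 83% from 25%, and it is wrong at the second look from 10% upward (34% or more). Sedation is named as a key adverse effect, and its background rate in this population is not stated and may not be low.

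**A symmetric p<0.001 boundary of the Haybittle-Peto type is a recognised choice**, and harm guidance is often placed in a committee charter, which is not at hand. Both points are fair and make this an improvement to a workable rule. They do not remove the point, because the protocol itself fixes the threshold for harm and uses mandatory wording.

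**A looser threshold brings false prompts.** This stands, and over many events and two looks it is more than negligible. The consequence is a committee review, not an automatic stop, and a short pre-named list of events limits it.

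**Conclusion.** The point holds in a limited form. The protocol requires the same p<0.001 for harm, adverse events included, as for benefit. For uncommon events this gives little sensitivity: a tripling from 5% or 10% is flagged with probability about 0.6% or 7% at the first look and about 5% or 34% at the second. For events with a background of 15% to 20% the first-look figures are 24% and 51%, so the rule is not generally inoperative. These figures rest on assumed event rates, a two-sided Fisher test and full evaluability; losses would lower them.

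The wording defect needs no assumption. A threshold stated as required in 11.6, 9.7 and the summary sits beside routes in 9.7 and 10.2 that have no threshold, and the passages must be reconciled.

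**What to change.** In 11.6, 9.7 and the trial summary, and in the committee charter if there is one:

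1. Keep p<0.001 as the boundary for benefit, on the primary outcome only.
2. For harm, replace the requirement with a less strict, non-binding statistical guide that prompts committee review, for example p<0.05 or p<0.01 on a short pre-named list of key adverse events, or on the primary outcome when it favours placebo. State whether the test is one- or two-sided.
3. State that p<0.001 does not limit a committee recommendation to stop for safety under 9.7 and 10.2.

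The cost is a change of wording and some unneeded reviews: about 0.7% to 1.5% per event per look at p<0.05 with background rates of 10% to 20%, and more across several events and two looks. The type I error for benefit is not inflated, because a prompt for harm can only lead to review or stopping and never to a claim of benefit. Even at p<0.05, a tripling from 5% would be flagged only about 15% of the time at the first look, so the guide supports the committee's judgement and does not replace it.

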12.0 ETHICS

12.1 Benefit anticipated from the study

At present, there is no medicine specifically approved for the treatment of delirium despite this symptom being relatively common in the palliative care setting, and the cause of considerable distress to patients, care givers and clinical staff.

This study therefore proposes to validate the use of a treatment that could provide significant improvement in symptom control where current treatments are not efficacious. The results of this study will provide evidence for the use of melatonin in this population, and if positive, may provide information to enable this medication to be submitted for approval by the Therapeutic Goods Administration and for listing on the Pharmaceutical Benefits Scheme for use in the community. If negative, given this is an adequately powered study that will help to inform clinical practice.

12.2 The possibility of physical stress or discomfort

Each of the study measures have been carefully selected to ensure they provide the best possible data with the least impact on the participant, and have been validated. As much as possible, the study measures are non-invasive in order to minimise physical stress.

Participants will be asked to provide a blood sample for baseline physiological measures. The taking of blood is uncomfortable, but short term. This is the only invasive procedure during the study period.

The study protocol is carefully planned to ensure that each participant's symptoms can be responded to by either increasing the study medication, and/or providing rescue medication that is currently used in clinical practice.

Side effects will be carefully monitored to ensure any anticipated discomfort is detected and treated in a timely manner.

12.3 The possibility of psychological stress or discomfort

Some participants may experience stress associated with completing some of the study measures. This is a vulnerable population, where sensitive issues about ability to continue to function, quality of life and other questions may raise broader issues of psychological distress.

Emotional distress caused by any of the questions in the quality of life measures will be dealt with by members of the palliative care team who would be involved either directly or in consultation with the care of the people under those circumstances. Although there may be acute distress, the weight of evidence is that such 'prompt' questions are in fact an avenue to open up discussions, which are well regarded by people despite their initial potential distress on occasion.

There will be no deception of participants at any stage of the project. Each participant interaction will be undertaken by carefully selected and trained study staff. This training will initially be undertaken in conjunction with investigators and senior research personnel, who have been trained in Good Clinical Practice, to ensure that staff are able to detect and monitor participant distress. Ongoing site monitoring will provide ongoing training opportunities.

12.4 Research on people in dependent relationships

The nature of doctor-participant relationships dictates that participants may feel that they are in the dependent position. The investigators and their designees will work to minimise any concern of inappropriate influence—the presentation of the study will be as unbiased as possible, the information sheet and consent forms will be clear, and participants will be able to withdraw from the study at any time. A person not directly involved in the clinical care of the participant will obtain consent. Each site will employ a recruitment nurse who will approach participants for permission to present the study. Each recruitment nurse will be trained in presenting the study in such a way that clinical care is separated.

12.5 Separation of research and clinical responsibilities

There are many distressing symptoms faced by participants with a life limiting illness and there is very little research to support many of the interventions that palliative medicine doctors provide daily around the world. Although research in this area poses its own unique dilemmas, the ethics of not conducting research into the best management of the dying participants is untenable. Importantly, participants will be cared for as individuals with specific needs; the needs of research will come second. Research staff, (medical or nursing), will clearly identify themselves and the purpose of their visit at their contact with the participant as being part of the research process. Training at the site initiation visit will provide an opportunity for study staff to determine appropriate ways of dealing with clinical situations that might arise during their research visits.

12.6 Method and nature of recruitment and advertising

Participants will be recruited on admission to the palliative care service and during initial screening in the participating clinics at each site. Advertising brochures will not be provided, only the information sheet and a verbal explanation. Any participant who is approached to take part in this study has the right of refusal. Refusal to take part in this study will not adversely affect the provision or quality of care provided to any participant in any way.

12.7 Protection of privacy and preservation of confidentiality

The participants will be allocated a unique ID number. The master list linking identifying participant information and ID number will be maintained in a locked cabinet, separate from the participant database. Form tracking will be via participant ID number only. There will be master lists held at each participating site and at the coordinating site at Flinders University in South Australia. The participant database will be stored on a password-

protected hard drive maintained by the study investigators. Data will be analysed by ID number only.

12.8 Restriction of use of data

Investigators will have access to data by ID number only for the purposes of data monitoring and analysis. The Project Officer will have access to all study data for the purposes of data checking, monitoring and preparation for analysis. Study project officers and site coordinators will have access to the local site Case Report Forms and the data contained within for the purposes of data collection, data entry and data query resolution. The Data Safety Monitoring Board will have access to de-identified data for safety and efficacy assessments. Study auditors will have access to Case Report Forms (by ID number only) and study files in order to audit the study. Site research ethics committees will have access to local data for audit purposes.

12.9 Use of personal information

Only enough personal information to give a general demographic and disease profile of the participant will be collected. The participant responses collected are limited to those that will address the study's primary and secondary aims.

12.10 Estimated time of retention of personal information and planned disposal

Records from the study will be maintained for 15 years after study completion in secure archiving facilities. Once the 15 year waiting period is complete, the files will be erased from the database hard-drive and any paper copies shredded, including the master list linking participant name and treatment number.

The data will be retained in accordance with good clinical practice recommended by the NHMRC National Statement and the CGP guidelines, and in a form that is at least as secure as the sources from which it was obtained.

13.0 STUDY ADMINISTRATION

13.1 Data handling and record keeping

The Palliative Care Clinical Studies Collaborative (PaCCSC) has a number of Standard Operating Procedure that will apply to all sites for the management of study data. Specifically the following Standard Operating Procedures apply;

- 5.5.1 Electronic Data Handling
- 5.23.2 CRF completion
- 8.0 Essential documents
- 8.4.1 Archiving of research/project materials
- 8.42 Record destruction

13.1.1 Direct access to source data:

A statement of permission to access source data for regulatory and audit purposes is included within the participant consent form with explicit explanation about this given as part of the consent process. Specifically, access will be required by study staff (including investigators, site coordinators and study nurses), Hospital Research Ethics Committees (HRECs), Data Safety Monitoring Committee (DSMC) and the PaCCSC data management team (National Project Officer and Administrative Officer) In addition de-identified data will be made available for meta-analysis and where requested by journals for publication purposes.

Case Report Forms will include:

- CRF Eligibility
- CRF Baseline
- CRF Intervention
- CRF Treatment Cessation
- CRF Withdrawal
- CRF Follow-up
- Medical Assessment and Screening Form

13.1.2 Data collection

Data will be sourced from the following;

Measure	Source	Completed by:
General demographic details	Clinical file	Study nurse
General Medical information	Clinical file	Medical officer
Concurrent medications	Clinical file	Medical officer
Pathology results	Pathology report	Pathology service
Vital signs	Clinical file	Study nurse
DRS-R-98	scale	Study nurse
DSM-V	CRF	Study nurse
NuDesc	scale	Study nurse
Insomnia Severity Index	scale	participant
RASS - Pal	CRF	Study nurse

13.1.3 Electronic recording

Study data will be recorded in a number of files for both the administration of the study and collection of participant data.

- 1. A master index will contain confidential participant contact information and will be the only link between individual participants and the ID number. This will be an Excel spreadsheet (Master patient index.xls).
- 2. The Forms Tracking index will be identified by ID number only. It will be used to track the data collection forms for each participant for auditing of data collection. It will contain dates of when each form is due, entered and finalised. (Forms tracking index.xls).
- 3. The Data file will be held and administered in the coordinating site, and will contain all the participant data as downloaded from the web site data forms. This data will then be transferred to the data set for analysis.

13.1.4 Data entry

Data will be entered from each site into a web-based interface specifically developed for this study. This password protected interface is protected behind a 'Ciskopix' firewall which helps prevent unauthorised access. No personally identifying information will be entered on this interface. The coordinating site will download the data on a regular basis as a comma delimited file.

On completion of data entry for each form, the study site will 'submit' the data, generating an automatic email sent to the project manager as part of the auditing process. The original form will be sent to the coordinating site for verification and then filed.

